4.3 TREATMENT PERIOD

Subjects who meet all eligibility criteria, as per data gathered from Screening Period are to be treated. All subjects who fail to meet eligibility criteria will be considered screen failure and exit the study without further evaluation

The maximum sample size for this study is 30 subjects that will be followed by treatment according to the schedule described above starting at Treatment Visit 1 (Week 1).

Treatment may continue until one of the following criteria applies:

- Disease progression,
- Intercurrent illness that prevents further administration of treatment,
- Unacceptable adverse event(s), or
- Withdrawal of consent

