5.1 REMOVAL OF SUBJECTS FROM STUDY TREATMENT AND/OR STUDY AS A WHOLE

Subjects can be taken off the study treatment and/or study as a whole at any time at their own request, or they may be withdrawn at the discretion of the investigator for safety, behavioral or administrative reasons. The reason(s) for discontinuation must be clearly documented on the appropriate eCRF and may include:

- Subject voluntarily withdraws from treatment (follow-up permitted)
- Subject withdraws consent (no follow-up permitted)
- Subject is unable to comply with protocol requirements
- Subject demonstrates disease progression
- Subject experiences unacceptable toxicity
- Treating physician determines that continuation on the study would not be in the subject's best interest
- Subject becomes pregnant
- Subject develops a second malignancy that requires treatment which would interfere with this study
- Subject becomes lost to follow-up (LTf)

If a subject fails to return for the scheduled study visit or is discontinued from the study, an attempt will be made to determine the reason(s). If the subject is unreachable by telephone, a registered letter will be sent to the subject requesting that he/she contact the clinic.

All patients with an ongoing SAE at the Post-Study (Follow-up) Visit (scheduled or premature) must be followed until the event is resolved (with or without sequelae) or deemed stable.

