6 STUDY TREATMENT

Eligible subjects will receive leronlimab (PRO 140) administered weekly at a dose of 525 mg SC until disease progression or intolerable toxicity.

Table 6-1: Treatment Administration Summary

Study Drug	Premedication	Dose	Route	Schedule	Supportive Therapies
Leronlimab (PRO 140)	N/A	525 mg	SC	Start on Week 1 and every week thereafter	N/A

Supportive care: Any required supportive care treatment such as antibiotics, anti- emetics, proton pump inhibitors and others will be given per institutional standards.

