6.1.5. Leronlimab (PRO 140) - Dose Modifications

The dose interruption and permanent discontinuation for any toxicity are described below.

Dose interruption: Refer to [Table 6-2](#) below. Recovery to acceptable levels must occur to allow leronlimab (PRO 140) continuation. Any adverse event deemed to be related to leronlimab (PRO 140) that requires a dose hold of more than 21 days will result in permanent discontinuation of leronlimab (PRO 140).

Table 6-2: Leronlimab (PRO 140) Dose Modification and Management for Injection Site Reactions

CTCAE Grade	Treatment Modifications
Grade 1	No dose adjustment is required.

Grade 2	First Occurrence: No dose adjustment is required. Second Occurrence of the same event: Closely follow-up for resolution of the AE to Grade ≤ 1
Grade 3	Withhold treatment until symptoms resolve to: • Grade 1 or less
Grade 4	Study treatment will be permanently discontinued

Permanent discontinuation of Treatment: If toxicity is reported at 525mg dose.

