9.2.6. Injection-site reactions

Injection-site reactions thought to be directly related to the injection are considered to be AEs of special interest, and will be assessed as per CTCAE v5.0.

For subjects who develop Grade 1 or Grade 2 events, therapy will be continued as per protocol. If a subject chooses to discontinue study treatment, the site should notify the protocol team leadership, and encourage the subject to complete any remaining study visits until the toxicity resolves.

For subjects who develop Grade 3 events following study drug injection, the subject should be reevaluated closely until the AE returns to Grade 1 or less, at which time study treatment may be reintroduced at the discretion of the site investigator. If the same Grade 3 AE recurs following the next administration of study drug, study treatment must be permanently discontinued. Subjects experiencing Grade 3 AEs requiring permanent discontinuation of study treatment should be followed closely for resolution of the AE to Grade 1 or less and the team leadership must be notified.

For Grade 4 events permanently discontinue therapy.

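### The last line of Protocol Section 6.1.5 permanently stops leronlimab for unqualified toxicity at 525 mg, the assigned dose, against Table 6-2, Section 9.2.6 and the hold rules in the same section

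*Protocol*

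**What the plan says.** Protocol Section 6.1.5 states that it covers both interruption and permanent discontinuation for toxicity of any kind. It contains, in order:

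- A recovery rule: leronlimab may continue once the toxicity has returned to an acceptable level.
- A hold rule: a leronlimab-related adverse event needing a hold of more than 21 days ends treatment.
- Table 6-2, titled for injection-site reactions. For Grade 1 and a first Grade 2 it says "No dose adjustment is required". A second Grade 2 is followed closely, Grade 3 is held until Grade 1 or lower, and Grade 4 is a permanent stop.
- The closing line: "Permanent discontinuation of Treatment: If toxicity is reported at 525mg dose".

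Section 9.2.6, also on injection-site reactions, says: "For subjects who develop Grade 1 or Grade 2 events, therapy will be continued as per protocol". After a Grade 3 reaction the subject is followed to Grade 1 or lower, "at which time study treatment may be reintroduced at the discretion of the site investigator". Treatment ends if the same Grade 3 event recurs after the next dose, or at Grade 4.

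Section 6 has leronlimab "administered weekly at a dose of 525 mg SC until disease progression or intolerable toxicity". The treatment-ending criteria in Section 4.3 include "Unacceptable adverse event(s), or", and the removal reasons in Section 5.1 include "Subject experiences unacceptable toxicity".

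**The concern.** The closing line is labelled as the permanent-discontinuation rule and names the dose that subjects are assigned. Nothing in the protocol ranks it below Table 6-2 or Section 9.2.6, so a site has two instructions for the same event.

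The conflict falls on events that should be expected. Section 1.4.3 reports that most adverse events in earlier leronlimab trials were mild or moderate. Section 1.4.5 reports that most injection-site reactions in study 1102 were mild and attributed to the drug.

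A site following the line to the letter would take a patient with advanced cancer off study drug for a mild reaction, while another site following Table 6-2 would carry on. With up to 10 centers, that difference would carry into the summary of adverse events leading to treatment discontinuation in SAP Section 8.3.1. That count would then reflect how sites read the rule as well as how the drug is tolerated.

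**Working it through.** The plan gives no figure to reproduce, so the check is a comparison of rules.

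**Who is covered.** Section 6 assigns 525 mg weekly, and Section 8.1 lists 525 mg as the only treatment group. Section 3 lets subjects enrolled under protocol version 1.0 stay on 350 mg. Those who do are outside the line; all others are inside it.

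**What happens to a subject on 525 mg.**

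| Event | Other rule | Closing line, literally | Result |
|---|---|---|---|
| Grade 1 injection-site reaction | Table 6-2: no change; 9.2.6: continue | Permanent stop | Conflict |
| Grade 2 injection-site reaction | Table 6-2: no change at first, close follow-up at second; 9.2.6: continue | Permanent stop | Conflict |
| First Grade 3 injection-site reaction | Table 6-2: hold to Grade 1 or lower; 9.2.6: may then restart | Permanent stop | Conflict |
| Same Grade 3 reaction after the next dose | 9.2.6: permanent stop | Permanent stop | Agree |
| Grade 4 injection-site reaction | Table 6-2 and 9.2.6: permanent stop | Permanent stop | Agree |
| Related event, hold of 21 days or less | 6.1.5: may continue after recovery | Permanent stop | Conflict |
| Related event, hold over 21 days | 6.1.5: permanent stop | Permanent stop | Agree |
| Toxicity not judged unacceptable or intolerable | 4.3 and 6: treatment may go on | Permanent stop | Line is stricter |

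The distinction between a first and a recurrent Grade 3 reaction comes from Section 9.2.6. Table 6-2 has a single Grade 3 row.

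**What this does to the rest of Section 6.1.5.** The recovery and 21-day rules matter only if some toxicities can be held and the drug resumed. If every toxicity at 525 mg is a permanent stop, neither rule has anything to decide at that dose.

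**Size.** The number of extra stops would be n × p × f, where n is the number of subjects on 525 mg, p the proportion with a toxicity that the other rules would let them continue through, and f the proportion of those handled literally. The documents give only an upper limit for n (30 enrolled, less any who stay on 350 mg). They give neither p for this population nor f. If f = 0 the effect is 0. No useful estimate follows.

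**The case against.** The strongest reply is that no experienced site would read the line literally. The graded table stands directly above it, Section 9.2.6 gives detailed instructions, and Sections 4.3, 5.1 and 6 all speak of unacceptable or intolerable events. The line probably lost a qualifier, or was meant to say that no lower dose is offered. This is fair on likelihood: nothing in the documents shows that literal stopping would be common. It does not remove the conflict. The line is an operative rule, and the reading that no lower dose exists still leaves undefined how severe a toxicity must be to end treatment.

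A second reply is that Table 6-2 and Section 9.2.6 concern injection-site reactions, so the direct grade-by-grade conflict is limited to those. That stands. Section 7.10 does cite Table 6-2 for toxicity of any kind, but the table's title says otherwise, and the point does not depend on settling that. The conflict with the recovery and 21-day rules is not confined to the injection site.

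A third reply concerns Sections 4.3 and 5.1. A reader might infer that they forbid stopping for anything less than an unacceptable event. They do not: Section 4.3 says treatment may continue until a listed event occurs, and the reasons in Section 5.1 are introduced as examples and include physician judgement. The closing line is stricter than their standard, but those sections alone would not rule out an earlier stop.

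**Conclusion.** The line is wrong as written. It contradicts the management of Grade 1, Grade 2 and first Grade 3 injection-site reactions, and it makes two rules in its own section redundant at 525 mg. This follows from the text alone and needs no assumed rates.

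The consequence is avoidable or inconsistent discontinuation, of unknown size. Three stronger readings are tempting and are not supported:

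- **A number of subjects lost.** Assuming 20 subjects and a 10% rate gives 20 × 0.10 = 2, and 30 subjects at 30% gives 30 × 0.30 = 9, or 2/30 = 6.7% to 9/30 = 30% of a Safety population of 30. Every input is assumed, and the answer is 0 if sites ignore the line. Earlier-trial proportions do not help. The 75% in study 1101 and 28 of 43 in CD01 count adverse events from any cause, in healthy volunteers and in subjects with HIV-1, under other regimens.
- **A misreported safety table.** If a site stops drug for a reported toxicity, the discontinuation summary correctly records that. The count would be higher than under Table 6-2, and harder to interpret, but not false. SAP Section 8.3 plans no inferential safety statistics.
- **A changed efficacy set.** Membership of the Evaluable population needs one dose and measurable disease at baseline, so stopping drug does not alter it. No Per Protocol effect is claimed.

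**What to change.** Replace the closing line of Section 6.1.5 with a rule to this effect: permanently discontinue leronlimab for (a) a Grade 4 injection-site reaction (Table 6-2); (b) recurrence of the same Grade 3 injection-site reaction after the next dose (Section 9.2.6); (c) a leronlimab-related adverse event requiring a hold of more than 21 days; or (d) any other adverse event judged unacceptable (Section 4.3).

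All four conditions are already in the protocol. The Grade 4 clause should stay limited to injection-site reactions. Subjects may be receiving chemotherapy or radiotherapy, and Section 9.2.3 attributes events to study treatment and to standard of care. A stop for every Grade 4 event whatever its cause would bring back the missing relatedness limit.

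Leave the title of Table 6-2 and the text of Section 7.10 as they are, so that management of systemic toxicity is neither removed nor extended. Whether Table 6-2 is meant to cover events away from the injection site is a separate question for the sponsor.

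The cost is a one-line protocol amendment with IRB approval under Section 11.3, which notes that an amendment may also require a consent-form change. No new data and no SAP change are needed.

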6.1.6. Leronlimab (PRO 140) - Disposition

All drug supplies are to be used only for this protocol and not for any other purpose. The investigator must not destroy any drug labels or any partially used or unused drug supply until instructed by the Sponsor. At the conclusion of the study and as appropriate during the course of the study, the investigator will return all used and unused drug containers and drug labels to the drug distributor as directed by the Sponsor. A copy of the completed drug disposition form will be sent to CytoDyn, Inc. or to its designee.

6.1.7. Leronlimab (PRO 140) - Accountability

Study drug must be used in accordance with this protocol and only under the direction of the responsible investigator. The investigational site must maintain complete and accurate records showing receipt and disposition of all study drug, including master records listing the date of receipt, the number and nature of medication units received, and a dispensing record which includes each quantity dispensed, identification of the staff member/subject to whom dispensed, the date of dispensing, the intended study participant, and the identification of the preparer. All used and unused study kits will be retained by the investigational site until drug accountability can be confirmed by study CRA during the monitoring visits. Instructions will be provided by Sponsor regarding final disposition of all study drug in compliance with applicable regulations.

6.1.8. Return and Retention of Study Drug

All unused investigational products will be disposed of according to the investigational site policy for standard of care drugs.

7 DESCRIPTION OF PROTOCOL ASSESSMENTS AND PROCEDURES

7.1 INFORMED CONSENT

A written informed consent will be obtained for this study for pre-screening and screening by the Investigator or designee from all subjects prior to performance of any protocol-specific procedure. This study will be conducted in accordance with the provisions of the Declaration of Helsinki.

The Investigator must comply with applicable regulatory requirements and must adhere to the Good Clinical Practice (GCP) in the process of obtaining and documenting the informed consent. The Investigator, or designee, must also inform subjects of all pertinent aspects of the study. Before written informed consent is obtained from the subject, the Investigator or a person designated by the Investigator, must provide the subject enough time and opportunity to inquire about the details of the study and to decide whether or not to participate in the trial. All questions addressed by the subject about the study must be answered to the satisfaction of the subject. Prior to the subject's participation in the trial, the written informed consent must be signed and personally dated by the subject and by the person who conducted the informed consent discussion. Authorization for release of protected health information must also be obtained, as per local policies.

7.2 ASSESSMENT OF ELIGIBILITY

The Investigator must assess subject' continued eligibility for the study as per the Inclusion and Exclusion criteria, during the Screening Period. The eligibility criteria are described in [Section 3.3.1](#) (Inclusion Criteria) and [Section 3.3.2](#) (Exclusion Criteria). In the event that the subject is not suitable or eligible for the study, the subject will be considered "screen failure".

7.2.1. Re-screening

If a subject fails initially to meet the eligibility criteria, and is later reconsidered for participation, the subject will be re-consented and assigned a new screening number at the time of re-screening. Subjects who fail their first screening attempt may be re-screened a maximum of once and may be enrolled in the study only if they meet all Inclusion and no Exclusion criteria when re-screened.

7.3 DEMOGRAPHIC INFORMATION AND BASELINE DISEASE CHARACTERISTICS

In this study the demographic information will include:

- Dates of ICF signature
- Date of birth
- Gender

- Race (American Indian/Alaskan Native, Asian, Black/African American, Native Hawaiian/Pacific Islander, Caucasian, or other)
- Ethnicity (Hispanic/Latino or Not Hispanic/Latino)

In addition, the following baseline disease characteristics will be collected:

- Year of initial diagnosis,
- Tumor morphology (Ductal/NOS, Lobular, Medullary, Tubular, Other, or Unknown),
- Histologic grade (I, II, III, or Unknown),
- Menstrual status,
- Location of metastasis (Brain, Visceral, Nonvisceral)

7.4 MEDICAL HISTORY

A complete review of the subject's past medical history, past surgeries, and current therapies (medications and non-medications) will be undertaken by the Investigator to check that all inclusion and no exclusion criteria have been met.

Events that emerge prior to the first treatment will be recorded in the medical history and not as AEs. Aside from being used to determine subject eligibility, this information will permit the Investigator to record the nature, duration and severity of any ongoing baseline medical conditions prior to the subject's receiving investigational product treatment.

Medical histories will be recorded using the body system categories outlined below:

• Cardiovascular	• Lymphatic
• Respiratory	• Hematologic
• Gastrointestinal	• Immunologic
• Renal	• Dermatologic
• Hepatic	• Psychiatric
• Neurological	• Genitourinary
• Endocrine	• Other

For each relevant history, the following will be documented:

- Disease/disorder/condition
- Date of diagnosis
- History status (resolved or ongoing).

7.5 CONCOMITANT MEDICATION

The subject may be applied any medications judged necessary by the Investigator, provided such medications are not listed in [Section 7.5.2](#).

All concomitant medication administered or taken by the subject beginning 30 days prior to Screening Visit and throughout the study will be recorded in the source documents and on the appropriate page of the Case Report Form (CRF) including all prescription, over-the-counter (OTC), herbal supplements, and IV medications and fluids. If changes occur during the trial period, documentation of drug dosage, frequency, route, and date may also be included on the CRF.

Subjects must be questioned at each study visit concerning any new medications or changes in current medications including over-the-counter medication and topical medication.

For each medication and non-study treatment, the following will be documented:

- Medication/treatment name (generic name may be used if trade name is unknown)
- Dose, unit, and frequency of dosing (individual dosages, not total daily dose).
- **Note:** Each new dose of medication should be recorded as a separate entry, with the exception of medications that are given on a sliding scale. For these, it is acceptable to enter the range of the dosage, including the start and stop dates for which the specified dosage range was used.
- Route of dosing
- Indication for use
- The start date
- The stop date (if medication/therapy is not ongoing).

7.5.1. Permitted Medications

All treatments that the investigator considers necessary for a subject's welfare may be administered at the discretion of the investigator in keeping with the community standards of medical care.

7.5.2. Prohibited Medications

Subjects are prohibited from receiving the following therapies during the Screening and Treatment Period of this trial:

- Investigational agents other than leronlimab (PRO 140)

7.6 VITAL SIGNS, HEIGHT AND WEIGHT

The following will be collected:

- Vital signs:
 - Seated blood pressure (taken after the subject has been seated for at least 5 minutes)
 - Pulse
 - Temperature (oral or tympanic)
 - Respiratory Rate
- Height (at Screening Visit only) and Weight
- BMI (derived from the height and weight measurements).

7.7 PHYSICAL EXAMINATION

The physical examination will include routine examinations for the following:

- Head, Ears, Eyes, Nose, Throat (HEENT)
- Abnormalities of the extremities
- Neurologic abnormalities
- Heart/cardiovascular abnormalities
- Musculoskeletal abnormalities
- Dermatologic abnormalities
- Any other body system for which an abnormality is noted and which, in the opinion of the Investigator, is relevant to the safety of the subject or could impact safety or efficacy results for the subject; i.e., the abnormality is clinically significant.

Each abnormality will be recorded and the Investigator will record an assessment of its clinical significance.

7.8 ECOG PERFORMANCE STATUS

The Eastern Cooperative Oncology Group (ECOG) performance status will be documented at the Screening Visit (SV), at the first treatment visit (T1) and every 3 weeks thereafter, and at End of Treatment (EOT) visit.

Table 7-1: ECOG Performance Status Scale

Grade	Description
0	Asymptomatic; Fully active, able to carry on all pre-disease performance without restriction
1	Symptomatic but completely ambulatory; Restricted in physically strenuous activity but ambulatory and able to carry out work of a light or sedentary nature, e.g., light house work, office work
2	Symptomatic, <50% in bed during the day; Ambulatory and capable of all selfcare but unable to carry out any work activities. Up and about more than 50% of waking hours
3	Symptomatic, >50% in bed, but not bedbound; Capable of only limited selfcare, confined to bed or chair more than 50% of waking hours
4	Bedbound; Completely disabled. Cannot carry on any selfcare. Totally confined to bed or chair
5	Dead

* As published in Am. J. Clin. Oncol.: *Oken, M.M., Creech, R.H., Tormey, D.C., Horton, J., Davis, T.E., McFadden, E.T., Carbone, P.P.: Toxicity And Response Criteria Of The Eastern Cooperative Oncology Group. Am J Clin Oncol 5:649-655, 1982.* The Eastern Cooperative Oncology Group, Robert Comis M.D., Group Chair.

7.9 ELECTROCARDIOGRAM (ECG)

A resting supine 12-lead ECG will be conducted at the Screening Visit (SV), at the first treatment visit (T1), and at End of Treatment (EOT) visit. A 12-lead EKG will be repeated during the study only if clinically indicated and at the discretion of the treating physician. The results will be evaluated by the Investigator. The following parameters will be recorded: ventricular rate (beats per minute), PR interval (msec), QRS interval (msec), QT interval (msec), and QTc interval (msec). Additionally, the Investigator will record the overall results of the ECG reading as either normal or abnormal, and as either not clinically significant or clinically significant. If abnormalities are observed, each will be recorded.

